#### **Analyses by body weight and dose group**

Patients who were randomized to secukinumab treatment arms (low dose and high dose) received secukinumab dose (75 mg, 150 mg or 300 mg) based on the weight categories (<25 kg, 25 to <50kg,  $\geq$ 50 kg). In addition to the planned secukinumab low dose and secukinumab high dose groups, further analyses will be performed for the below groups by body weight and secukinumab dose:

- AIN457 75 mg and < 25 kg
- AIN457 75 mg and 25-<50 kg
- AIN457 150 mg and 25-<50 kg
- AIN457 150 mg and  $\geq$ 50 kg
- AIN457 300 mg and  $\geq$ 50 kg

For PASI 50, PASI 75, PASI 90, PASI 100 and IGA 0 or 1 response, the missing data will be imputed by pure non-responder imputation method.

#### **Analyses by IRT dosing error, body weight and dose group**

Analyses will be performed for IRT error affected and not affected patients within the groups by body weight and secukinumab dose. The treatment groups will be:

- AIN457 75 mg and 25-<50 kg Not affected
- AIN457 150 mg and 25-<50 kg Affected
- AIN457 150 mg and 25-<50 kg Not affected
- AIN457 150 mg and  $\geq$ 50 kg Affected
- AIN457 150 mg and  $\geq$ 50 kg Not affected
- AIN457 300 mg and  $\geq$ 50 kg Affected
- AIN457 300 mg and  $\geq$ 50 kg Not affected

For PASI 50, PASI 75, PASI 90, PASI 100 and IGA 0 or 1 response, the missing data will be imputed by pure non-responder imputation method.

#### **Analyses by age strata excluding IRT dose affected subjects**

A figure will be provided for PASI 75, PASI 90, PASI 100 and IGA 0 or 1 response over time, by age stratum, excluding IRT dose affected subjects. Missing data will be imputed by pure non-responder imputation method.

### **Analyses treating the IRT dose error affected results as missing**

Analyses will be performed for PASI 75, PASI 90, PASI 100 and IGA 0 or 1 response over time, treating the IRT dose error affected results as missing. Frequency and percentage of subjects will be provided, also a figure will be provided.

## **5 Appendix**

### **5.1 Documentation of statistical methods**

Summary statistics for continuous variables will include N, mean, standard deviation, minimum, lower quartile (Q1), median, upper quartile (Q3), maximum. Summary statistics for discrete variables will be presented in contingency tables and will include absolute and relative frequencies.

#### **5.1.1 Analysis of continuous data**

Summary statistics (including N, mean, standard deviation, minimum, lower quartile (Q1), median, upper quartile (Q3), maximum) will be provided for continuous data by visit and treatment group. For PASI score, CDLQI total scores, summary statistics will be derived for absolute and percentage changes from baseline.

#### **5.1.2 Analysis of binary (and categorical) data**

##### **5.1.2.1 Summary statistics for binary and categorical data**

Summary statistics for discrete variables will be presented in contingency tables and will include absolute and relative frequencies. If applicable, confidence intervals will be derived as well based on the score method including continuity correction [[Newcombe \(1998\)](#)]:

With  $z$  as (1-alpha/2)-quantile of the standard normal distribution (SAS:  $z=PROBIT(1-\alpha/2)$ ),  $n$  as total number of subjects (i.e. number of subjects in the denominator), and  $p$  as estimated crude incidence (number of subjects with event /  $n$ ) it is  $q=1-p$

Then the lower limit is for  $p > 0$ , ( $L = 0$  for  $p = 0$ ),

$$L = \max \left( 0, \frac{2np + z^2 - 1 - z\sqrt{z^2 - 2 - 1/n + 4p(nq + 1)}}{2(n + z^2)} \right)$$

and the upper limit is for  $p < 1$ , ( $U = 1$  for  $p = 1$ ),

$$U = \min \left( 1, \frac{2np + z^2 + 1 + z\sqrt{z^2 + 2 - 1/n + 4p(nq - 1)}}{2(n + z^2)} \right)$$

For response variables (e.g. for IGA mod 2011 0 or 1, PASI 75 and PASI 90 response) the placebo-adjusted response rates including exact 95% confidence intervals (using the RISKDIFF option in PROC FREQ) will be derived.

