## 2.6.4 Handling of missing values/censoring/discontinuations

The following imputation methods will apply to the missing data for analysis up to Week 52 including primary W12 analysis:

- Response variables based on PASI score and IGA mod 2011 categories will be imputed with multiple imputations (MI) method as primary imputation method. Multiple imputation (MI) is a simulation based approach where missing values are replaced by multiple Bayesian draws from the conditional distribution of missing data given the observed data and covariates, creating multiple completed data sets. These completed data sets can then be analyzed using standard methods. Within this analysis, the PASI score or

IGA mod 2011 categories will be imputed and response variables will be derived based on the imputed scores. In the multiple imputation analysis, the response status will be imputed based on the individual treatment arm information.

- (Pure) Non-responder imputation will be used as a sensitivity method: Missing values with respect to response variables based on PASI score and IGA mod 2011 categories will be imputed with non-response regardless to the reason for missing data. Subjects with missing baseline or those with all post-baseline missing will be imputed with non-response.

[REDACTED]

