### 2.7.3 Other Efficacy variables

## PASI 75, PASI 90, PASI 100 and IGA 0 or 1 response over time

Summary statistics for PASI 75, PASI 90, PASI 100 and IGA 0 or 1 response by visit will be presented in contingency tables and will include absolute and relative frequencies.

Confidence intervals for response rates will be derived as well.

For PASI 75, PASI 90, PASI 100 and IGA 0 or 1 response at each visit, each secukinumab dose regimen will be compared to placebo (up to Week 12 only) [REDACTED] by exact logistic regression with treatment group, baseline bodyweight stratum, age stratum and baseline PASI score as explanatory variables.

For PASI 75, PASI 90 and IGA 0 or 1 response, the placebo-adjusted response rates including 95% confidence interval will be derived by visit up to Week 12. [REDACTED]

Additional summary analysis will be performed for PASI and IGA response by IRT dosing error and by body weight and dose group. See [Section 4.1](#) for details.

Figures will also be provided.

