### 5.1.2.3 Multiple imputations for response variables

PASI 75 and IGA 0 or 1 response at Week 12 will be evaluated using an exact logistic regression model with treatment group baseline body weight stratum, age stratum and

baseline PASI as effects with multiple imputations for missing values. In addition, exact logistic regression analysis for PASI 50, PASI 75, PASI 90, PASI 100 and IGA mod 2011 0 or 1 response by visits will be analyzed using multiple imputation method.

Summary statistics for PASI 50, PASI 75, PASI 90, PASI 100, and IGA mod 2011 0 or 1 response by visit will be presented in contingency tables with multiple imputations method.

In the multiple imputations analysis, the response status will be imputed based on the individual treatment arm information.

In case of higher drop-out rates or higher study treatment discontinuations for reasons other than lack of efficacy, additional sensitivity analyses will be performed.

Multiple imputation (MI) is a simulation based approach where missing values are replaced by multiple Bayesian draws from the conditional distribution of missing data given the observed data and covariates, creating multiple completed data sets. These completed data sets can then be analyzed using standard methods. [Rubin \(1987\)](#) presented rules how to combine the multiple sets of estimates to produce overall estimates and confidence intervals that adequately incorporate missing data uncertainty.

Missing values for the 'PASI score', 'IGA mod 2011 score', 'change from baseline PASI score' and 'change from baseline IGA score' will be imputed simultaneously based on an underlying normal distribution and using a Markov Chain Monte Carlo (MCMC) method. The change from baseline in PASI score appears to follow closer to a normal distribution than the actual PASI score. Assuming normality for the 'IGA mod 2011 score' is motivated by [Schaefer \(1997\)](#), where it was shown that the multivariate normal approximation for the imputation of incomplete categorical and binary data is robust.

The imputations will be done separately for each treatment group including baseline weight, and number of previous systemic therapies as additional covariates.

The number of imputations will be set to 100, the seed for the random function will be set to 4572310 for this study. To generate the multiple imputed data sets, the SAS procedure MI can be used as follows:

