estimate=exp(ESTIMATE);
LCLMEAN=estimate*exp(-1.96*stderr);
UCLMEAN=estimate*exp(+1.96*stderr);
RUN ;
```

In case if exact logistic regression does not converge and risk difference estimates will be provided. The SAS procedure PROC FREQ for risk difference estimates will be applied as follows:

```
ODS LISTING CLOSE;
PROC FREQ DATA=<Imputed dataset> ORDER=DATA;
  TABLES <treatment group>*<response variable>/riskdiff fisher alpha=0.05;
  BY <By-variables>;
  ODS OUTPUT RiskDiffCol1=RiskDiffCol1 FishersExact=fisherexact;
RUN;

ODS LISTING;
DATA DRISK; SET RiskDiffCol1;
  WHERE control="1";
  ESTIMATE=risk;
  STDERR=ase;
  effect="Riskdiff";
```

```
IF missing(ESTIMATE) OR missing(STDERR) THEN DELETE;  
RUN;  
  
PROC SORT DATA=DRISK; BY <By-variables>; RUN;  
ODS LISTING CLOSE;  
ODS OUTPUT ParameterEstimates=results VarianceInfo=varinfo ModelInfo=Modelinfo;  
PROC MIANALYZE PARAMS=drisk;  
  by <By-variables>;  
  modeleffects Riskdiff;  
  stderr ase;  
RUN;  
  
ODS LISTING;  
DATA results2;  
  set results;  
  or=estimate*100;  
  lowercl=(LCLmean)*100;  
  uppercl=(UCLmean)*100;  
  KEEP <response variable> <By-variables> or lowercl uppercl probt;  
RUN;
```

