### 5.1.3.4 Risk difference and 100\*(1- $\alpha$ )% confidence interval

For an investigational drug group with  $n_1$  subjects at risk, independent from the control group (e.g., placebo or comparator) with  $n_0$  subjects at risk, of whom  $x_1$  and  $x_0$  experience a certain event, the risk difference is estimated as  $p_1-p_0$  with  $p_1=x_1/n_1$  and  $p_0=x_0/n_0$ .

Exact unconditional confidence limits for the risk difference will be obtained with SAS procedure PROC FREQ and option RISKDIFF in the TABLES statement, specifying the RISKDIFF option also in the EXACT statement.

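### Under multiple imputation the SAP gives PASI and IGA response rates only complete-data intervals, and reserves its pooled risk difference for fallback cases

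*SAP*

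**What the plan says.** - **Missing data.** SAP 2.6.4 states that PASI and IGA responses up to Week 52, including the Week 12 primary analysis, "will be imputed with multiple imputations (MI) method as primary imputation method". SAP 5.1.2.3 adds: "The number of imputations will be set to 100".
- **Tables.** SAP 5.1.2.3 says that PASI 50/75/90/100 and IGA 0 or 1 "response by visit will be presented in contingency tables with multiple imputations method". SAP 2.7.3 asks for intervals for the rates and says that "the placebo-adjusted response rates including 95% confidence interval will be derived by visit up to Week 12". It names no method for either.
- **Single rates.** SAP 5.1.2.1 says, where applicable, "confidence intervals will be derived as well based on the score method including continuity correction", with p defined as the number of subjects with the event divided by n.
- **Differences from placebo.** SAP 5.1.2.1: "the placebo-adjusted response rates including exact 95% confidence intervals (using the RISKDIFF option in PROC FREQ) will be derived". SAP 5.1.3.4: "Exact unconditional confidence limits for the risk difference will be obtained with SAS procedure PROC FREQ". Protocol 9.4.2 and 9.5.2 also specify the exact method.
- **Pooled route.** SAP 5.1.2.3 cites Rubin's rules as the way to obtain intervals that reflect missing-data uncertainty. It codes a risk difference and its asymptotic standard error per imputation, combined with PROC MIANALYZE, under the heading "In case if exact logistic regression does not converge and risk difference estimates will be provided". SAP 2.6.3 adds a second trigger: a response rate of 0% or 100% in a treatment group.

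**The concern.** Response rates and their differences from placebo are how most readers will take in the co-primary results. The odds ratio beside them is meant to carry imputation uncertainty through Rubin's rules. The rates, as specified, do not: with the MI-averaged p and full n, an arm with 30% of its values imputed gets essentially the same interval width as a complete arm.

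For differences the problem is one of application. Exact limits are built from integer counts in one 2×2 table. They supply no standard error to pool, and the MI-averaged count is usually not an integer. A programmer would have to improvise. The risk-difference method could also change between visits and endpoints, depending on whether a logistic model converged.

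**Working it through.** **Inputs.** From the sample-size section (SAP 3): 40 subjects per group, placebo rate 10%, secukinumab rates 65% (PASI 75) and 45% (IGA). From SAP 5.1.2.3: m = 100. Assumed, because the documents give no rate: missing fraction f of 5%, 10%, 20% or 30%, missing completely at random, no auxiliary variables in the imputation.

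**The plan's own figures.** The SAP states no figure for these intervals. Its power figures reproduce by full enumeration of Fisher's exact test at 1.25% one-sided: 99.9%, 88.4% and 82.1%, against the stated 99%, 88% and 82%. The design inputs are therefore sound.

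**Step 1: the stated score interval.** With q = 1 − p and z = 1.96:

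L = [2np + z² − 1 − z√(z² − 2 − 1/n + 4p(nq + 1))] / [2(n + z²)]

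U = [2np + z² + 1 + z√(z² + 2 − 1/n + 4p(nq − 1))] / [2(n + z²)]

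For 26/40 (n = 40, p = 0.65):

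- L = (52 + 3.84 − 1 − 1.96√40.82) / 87.68 = 0.483
- U = (52 + 3.84 + 1 + 1.96√39.62) / 87.68 = 0.789
- Width 0.306. Nothing in either limit depends on how many of the 40 values were imputed.

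**Step 2: what Rubin's rules add.** Total variance T = W + (1 + 1/100)B. Without auxiliary information B = W·f/(1 − f), so the standard error grows by √(1 + 1.01·f/(1 − f)), which is 1.026, 1.055, 1.119 and 1.197 at 5, 10, 20 and 30% missing. Putting effective n = 40(1 − f) into the Step 1 formula for p = 0.65 gives widths 0.314, 0.323, 0.342 and 0.364, against 0.306.

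**Step 3: simulation of a single rate.** 20,000 arms of 40 per setting, 100 imputations each from a Beta posterior. The stated interval uses the MI-averaged p and n = 40. The comparator is the same score formula with effective n = p(1 − p)/T.

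| Missing | True rate 65%: stated → with T | Ratio | True rate 10%: stated → with T | Ratio |
|---|---|---|---|---|
| 5% | 0.303 → 0.310 | 1.023 | 0.209 → 0.217 | 1.038 |
| 10% | 0.303 → 0.318 | 1.050 | 0.209 → 0.224 | 1.072 |
| 20% | 0.303 → 0.336 | 1.109 | 0.209 → 0.241 | 1.153 |
| 30% | 0.303 → 0.356 | 1.175 | 0.209 → 0.261 | 1.249 |

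Across true rates and repeat runs the shortfall in width is about 2–4%, 5–8%, 11–16% and 18–25%.

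Coverage of the stated interval at true rates of 10, 45 and 65% was 95.7–97.6% at 5–10% missing, 93.8–96.2% at 20% and 92.4–94.2% at 30%. A separate run over true rates of 10–80% gave 92.7–94.6% at 30%. The continuity correction absorbs the omitted variance when little is missing.

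**Step 4: differences.** In the simulation the MI-averaged responder count was not an integer in about 98–99.9% of data sets with missing values, so exact 2×2 limits cannot be run on it directly. For scale, take 26/40 against 4/40:

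- Exact unconditional limits: 0.336 to 0.722, width 0.386.
- Complete-data Wald width: 3.92 × √(0.65·0.35/40 + 0.10·0.90/40) = 0.349.
- Rubin-pooled Wald width: 0.358, 0.368, 0.391 and 0.418 at 5, 10, 20 and 30% missing.

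The exact interval is wider than the pooled one up to 10% missing, about equal at 20% and narrower at 30%. This compares widths in one example; coverage of the difference was not computed.

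**The case against.** The strongest reply is that this is an omission of scope. SAP 5.1.2.1 is generic text for all binary data and nowhere instructs anyone to insert an MI-averaged p with full n. The SAP does contain a pooled risk difference. The score and exact intervals are correct for the non-responder-imputed analyses. SAP 2.1 says the 95% intervals are for estimation and not for decisions. The simulation also ignores the baseline covariates and earlier PASI and IGA values in the SAP's imputation model, which would reduce between-imputation variance.

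All of that stands and limits the size. It does not remove the gap: no MI interval for a single rate appears anywhere in the SAP, and the pooled difference is confined to two fallback triggers.

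A reader might go further in five ways that the documents do not support:

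- **All these intervals are too narrow once any value is imputed.** Single-rate coverage stays above 95% up to 10% missing, and narrowness is not shown for the exact difference.
- **Exact limits cannot be pooled at all.** They cannot be pooled by Rubin's rules; the SAP names no other rule.
- **Differences from placebo deteriorate towards Week 52.** They exist only up to Week 12.
- **Missingness at Week 12 is known to be high.** SAP 4.1 reports Week 12 visits delayed beyond Day 88, but gives no count.
- **The unadjusted difference is itself an error.** A crude difference beside a stratum-adjusted odds ratio is valid; a Mantel-Haenszel version would be a separate preference.

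**Conclusion.** The point holds in limited form. For single response rates, the only stated interval omits between-imputation variance and so falls short of the SAP's own aim for MI intervals. The effect is small at 5–10% missing (width short by about 2–8%, coverage still above 95%). It is moderate at 20% (11–16%, coverage about 94–96%) and material at 30% (18–25%, coverage about 92–95%). These sizes rest on 40 per arm, data missing completely at random, no auxiliary variables and an assumed missing rate; the actual loss at a given missing rate should be smaller because the imputation model has informative covariates.

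For placebo-adjusted rates, available to Week 12 only, the defect is that the stated method does not apply to MI data. No hypothesis test depends on any of these intervals.

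**What to change.** 1. **Single rates under MI.** State that each rate is pooled by Rubin's rules at every visit, either on the logit scale or as a score interval with effective n = p(1 − p)/T. Give a rule for a rate of 0% or 100%, where the logit is undefined. At the assumed 8% placebo PASI 90 rate, no responders among 40 has probability 0.92⁴⁰ ≈ 3.6%.
2. **Placebo-adjusted rates under MI.** Use the SAP 5.1.2.3 pooled risk difference for every visit up to Week 12, not only after non-convergence or a 0%/100% rate.
3. **Other tables.** Keep the score and exact intervals for non-responder-imputed and observed-case tables.
4. **Record the change.** Note it in SAP section 4 as a departure from the exact method in Protocol 9.4.2 and 9.5.2. Section 9.5.2 asks for exact limits for single rates as well, so the note should cover both.

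**Cost.** A few sentences and a short program; the risk-difference code exists. Single-rate intervals become slightly wider where data are missing. The pooled difference uses an asymptotic standard error, so it gives up the exact guarantee and may be narrower than exact limits when little is missing.

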### 5.1.2.2 Exact Logistic regression

Selected binary outcome variables including PASI 50 / 75 / 90 / 100 response and IGA mod 2011 0 or 1 response, will be evaluated using an exact logistic regression model with treatment regimen, age category, baseline body weight category and baseline score for the response variable. Remove “baseline score for the response variable” from the exact logistic regression model, if model doesn’t converge or have insufficient SAS memory issue while executing the model. Odds ratios will be computed for comparisons of secukinumab dose regimens versus control(s) utilizing the exact logistic regression model fitted.

Additional exact logistic analysis will be performed for IRT dosing error subjects, using both multiple imputation and pure non-responder imputed records.

If response rates are 0% or 100% in one of the treatment groups then odds ratio estimates and p-values will not be displayed in outputs, but “-” will be shown.

The odds ratio will be calculated such that an odds ratio  $> 1$  is favorable for secukinumab. Using PROC GENMOD with EXACT statement to calculate the confidence interval for the odds ratios conditional on all other parameters specified in MODEL statement. The 95% confidence interval for the regression parameter of the active treatment effect relative to control(s) will be calculated using an exponential transformation to create the confidence interval for the odds ratio.

All p-values reported on linear hypotheses about regression coefficients will be based on the exact tests in the SAS procedure PROC GENMOD with EXACT statement.

For superiority hypotheses, one sided p-value will be calculated by dividing the two-sided p-value by half (i.e., “p/2”) if treatment effect is in favor of secukinumab dose regimens and calculated by “1-p/2” if treatment effect is in favor of Control.

Exact logistic regression will be applied to response variables at each visit.

If exact logistic regression model does not converge, then the following steps will be performed:

- If convergence not reached, remove the covariates from the model one by one until convergence is reached; start with continuous covariates (i.e., baseline PASI), followed by removing categorical covariates (i.e., age, bodyweight strata);
- If convergence not reached at all, then perform Fisher’s exact test.

It should be noted that this model might not converge if response rates are too low.

Of note, for the subgroup analysis by body weight or age stratum, the weight stratum or age stratum variable will not be fitted in the exact logistic regression model.

